### 9.5.3 Adverse Event Reporting

For the purposes of this study, the period of observation for collection of AEs begins after the first dose is administered and continues through the completion of the study at Week 14 (end of treatment). Any health changes prior to first dose will be recorded as medical history.

All AEs occurring during the study will be individually assessed by the Investigator, reported, and recorded, regardless of seriousness or relationship to the study product.

The following information will be documented in each case:

- Participant ID
- AE Term

	Protocol 812P413	
	Page 43 of 61	Version 2.0

- Start Date of event
- End Date of event or Ongoing
- Severity or Intensity
- Seriousness
- Action taken with study product
- Action taken to treat event
- Outcome
- Relationship to study product
- Participant's health status

#### 9.5.4 Serious Adverse Event Reporting

Documentation of an SAE requires that in addition to AE information provided in [Section 9.5.3](#), the Investigator or designee will provide:

- Seriousness criteria: life threatening, hospitalization, persistent/significant disability, congenital anomaly/birth defect, death [if marked, then date of death]
- Event Description: where a narrative would capture the details of the event
- Relevant Medical History: any medical history pertinent to the event
- Other situations:
  - Medical or scientific judgment will be exercised by the Investigator in deciding whether SAE reporting is appropriate in other situations, such as significant medical events that may jeopardize the participant, and/or may require medical or surgical intervention to prevent one of the other outcomes listed in the above definition. These events should usually be considered serious.
  - Examples of such events include invasive or malignant cancers, intensive treatment for allergic bronchospasm, blood dyscrasias, convulsions or development of intervention dependency or intervention abuse.

In addition, the Sponsor (via the Investigator or designee) will be notified of SAE via email within 24 hours of identifying it ( e.g. recorded in the SAE form). SAE meeting the Institutional Review Board (IRB) criteria for reporting will be reported to the IRB within the required timeline. SAEs which result in death or are life-threatening must be reported to IRB and Sponsor immediately.

#### 9.5.5 Adverse Event Severity and Causality Assessments

##### Assessment of Severity

The severity of AEs will be defined by the following criteria.

- *Mild*: Symptoms hardly perceived, only slight impairment of general well-being
- *Moderate*: Clearly noticeable symptoms, but tolerable without immediate relief
- *Severe*: Overwhelming discomfort

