#### Expected Adverse Events

Expected AEs are known AEs based on previous findings from use of the products or procedures used in this study. The most commonly observed adverse reactions in adults are insomnia, headache, somnolence, fatigue, nausea, decreased appetite, dry mouth and constipation ([Qelbree PI](#)).

Adverse events of concern include (1) suicidal thoughts and behavior, (2) blood pressure and pulse rate increases, (3) activation of mania or hypomania, and (4) somnolence and fatigue ([Qelbree PI](#)).

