8.1. Adverse Events

All adverse events (AEs) will be coded using the MedDRA Version 27.0 or current version.

A treatment-emergent adverse event (TEAE) is defined as an AE with a start date on or after the first dose of study medication, or that worsened in severity following the first dose of study medication. Any event that is present at baseline but worsens in severity will be determined by the Investigator and entered in the eCRF as a new AE. Thus, AEs that occurred on or after the first dose of study medication are TEAEs.

The incidence of TEAEs (number and percent of subjects) will be summarized by System Organ Class (SOC), preferred term (PT), and treatment groups. It will be sorted by decreasing frequency for the overall active treatment groups. A subject with multiple occurrences of an AE with the same PT will be counted only once in the AE category per SOC and PT for summary tables. In addition, for TEAE tables that are summarized by PT and treatment group, the sorting will be based on the decreasing frequency within the PT.

Based on the investigator's determination, the severity of TEAEs will be classified as mild, moderate or severe. For summaries by severity, a patient experiencing multiple AEs in the same PT with different intensities will only be counted once with the maximum severity. If severity is missing, then the maximum severity will be assumed for the analysis (i.e., severity = severe).

The relationship between the study medication and a TEAE is determined by the investigator and will be classified as unrelated (i.e., unlikely related or not related) or related (possibly related, probably related or definitely related). TEAEs with missing relatedness will be counted as definitely related. For summaries by relationship, a patient experiencing multiple AEs in the same PT with different relationship will only be counted once with the most related occurrence.

An overview of TEAEs will include summaries of incidence rates of subjects who had at least one TEAE, serious TEAE, TEAE leading to death, TEAE by maximum severity, TEAE by relationship, TEAE leading to withdrawal of study medication and related serious TEAE.

In addition to the overview of TEAE summary, the following summary tables will be provided:

- Treatment-Emergent Adverse Events by System Organ Class and Preferred Term
- Most Common ($\geq 5\%$) Treatment-Emergent Adverse Events by Preferred Term

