- Treatment-Emergent Adverse Events by System Organ Class, Preferred Term, and Maximum Severity
- Treatment-Emergent Adverse Events by System Organ Class, Preferred Term, and Relationship to Study Medication
- Serious Treatment-Emergent Adverse Events by System Organ Class and Preferred Term
- Treatment-Emergent Adverse Events Leading to Withdrawal of Study Medication by System Organ Class and Preferred Term

In addition, listings will be provided for TEAEs, SAEs, TEAEs Leading to Withdrawal of Study Medication, and Deaths. If no SAEs or Deaths occurred, a blank listing with “No SAE (or Deaths) were reported on this study” will be indicated in the listing.

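### AE severity grades rest on perceived symptoms and discomfort and are not exhaustive, so the maximum-severity tables may under-grade BP/pulse and mania/hypomania events

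*Protocol*

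**What the plan says.** Protocol 9.5.5 (Assessment of Severity) gives three criteria by which AE severity is to be defined:

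- Mild: "Symptoms hardly perceived, only slight impairment of general well-being"
- Moderate: "Clearly noticeable symptoms, but tolerable without immediate relief"
- Severe: "Overwhelming discomfort"

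The same section, under Expected Adverse Events, lists the events to watch: "Adverse events of concern include (1) suicidal thoughts and behavior, (2) blood pressure and pulse rate increases, (3) activation of mania or hypomania", with somnolence and fatigue as the fourth.

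SAP 8.1 uses no other scale. It says "Based on the investigator's determination, the severity of TEAEs will be classified as mild, moderate or severe", and that "a patient experiencing multiple AEs in the same PT with different intensities will only be counted once with the maximum severity". The planned outputs include maximum severity in the TEAE overview and a table titled "Treatment-Emergent Adverse Events by System Organ Class, Preferred Term, and Maximum Severity". A missing grade is counted as severe.

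**The concern.** A severity scale should give every event one grade and let a worse event receive a higher one. This scale refers to perception, general well-being, tolerability and discomfort. It does not refer to the size of a measured finding, to interference with usual activities beyond the well-being phrase in Mild, or to clinical significance. Two of the AEs of concern can be important without being felt: a BP or pulse rise found on the home cuff, and an elevated mood state that the participant does not find unpleasant.

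What is at stake is the descriptive safety account. Protocol 3.3.1 and 3.3.3 summarise previous safety experience by saying that most events were mild or moderate, and this single-arm study invites the same sentence. For symptom-free events on this scale, that sentence would be partly true by definition.

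**Working it through.** No figure in the plan stands behind the scale, so the check is a reading of the three definitions against possible events.

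**1. Coverage.** Cross the intensity of symptoms with the need for immediate relief:

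| Intensity | Tolerable without immediate relief | Needs immediate relief |
|---|---|---|
| Hardly perceived | Mild | Mild |
| Clearly noticeable, not overwhelming | Moderate | no grade |
| Overwhelming | Severe | Severe |

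One cell is empty. An investigator must either give Moderate against its own condition or give Severe against its own condition. The result then depends on the rater.

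**2. Symptom-free measured findings.** Moderate requires clearly noticeable symptoms and Severe requires overwhelming discomfort. A BP or pulse AE without symptoms meets neither, so only Mild is open to it, whatever the reading.

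**3. Events without discomfort.** Mania or hypomania with clearly noticeable symptoms can be Moderate. Severe is defined by discomfort alone, so an episode without discomfort is capped below Severe however much it impairs the person.

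**4. Do other planned outputs fill the gap?**

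- *BP and pulse.* SAP 8.2.1 summarises observed values and change from baseline by visit, and the statistics in SAP 5.1 include the maximum. This shows the largest change but not how many participants had a large one. The shift tables in SAP 8.2.2 use fixed ranges: pulse 50 to 100, diastolic 60 to 90. A pulse going from 65 to 90 is a rise of 90 − 65 = 25 bpm, yet it is normal to normal and shows no shift. A diastolic value going from 70 to 88 is a rise of 18 mmHg and also shows none. Protocol 3.3.1 describes this risk by rises above 20 bpm and of at least 15 mmHg. The SAP has no table on those thresholds.
- *Mania/hypomania.* Protocol 3.3.3 says participants will be monitored for it, but the schedule (Table 1) has no mania scale after screening and the SAP plans no separate summary. Apart from seriousness, withdrawal and listings, the AE grade is the planned measure of how bad an episode was.
- *Suicidality.* C-SSRS categories are tabulated by visit (SAP 8.3) and do not depend on the grade.
- *Somnolence and fatigue.* These are felt symptoms, and the scale can grade them.
- *Treatment of the event.* It is recorded for each AE (Protocol 9.5.3) but appears in none of the summary tables listed in SAP 8.1.

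The weakness therefore bears on two of the four AEs of concern.

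**5. Size.** Protocol 3.3.1 gives threshold crossings at any time in the 6-week adult trial. Scaled to 750 dosed (Protocol 12.3), assuming the same rates:

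- pulse rise above 20 bpm: 52/178 = 29.2%, and 750 × 52/178 ≈ 219 (placebo 23/181 = 12.7%)
- diastolic rise of at least 15 mmHg: 23/178 = 12.9%, and 750 × 23/178 ≈ 97 (placebo 16/181 = 8.8%)

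These are measurements, not AEs. The documents do not say how many such rises would be reported as AEs or would be symptom-free, so the number of these participants with an under-graded AE could lie anywhere from 0 to the counts shown. The nearest AE rate in the protocol is tachycardia at 4% (Protocol 3.2.2), or 0.04 × 750 = 30, again with the symptom-free share unknown.

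**The case against.** The best defence is that the severity table is not where these risks are mainly reported. BP, pulse and C-SSRS are safety endpoints in their own right and are analysed without the AE grade. Serious TEAEs and TEAEs leading to withdrawal have their own tables, and seriousness is judged on outcome and medical judgement (Protocol 9.5.2), so a manic episode that leads to hospitalisation would be caught there. Bipolar disorder is an exclusion. The study is descriptive, with no hypotheses. All of this is correct and limits the consequence. It does not repair the grade, and the alternatives leave the gaps shown in the working. Seriousness also does not rank non-serious events.

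A reader might infer more than the documents support:

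- *That hypomania must be graded Mild.* It need not be. Noticeable symptoms fit Moderate, and the text does not say to whom they must be noticeable. Only the cap below Severe follows.
- *That any event needing treatment is ungraded.* The condition in Moderate is immediate relief. Headache or insomnia treated without urgency still fits Moderate.
- *That ungraded events will be left blank and then counted as severe.* Protocol 9.5.3 requires severity to be documented for each AE, and nothing suggests that a borderline event would be left without a grade.
- *That the counts of 219 and 97 are misgraded AEs.* They are threshold crossings, and crossings also occurred on placebo.

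**Conclusion.** The point holds as a defect in the definitions. By their terms, a symptom-free BP or pulse AE can only be Mild, an event without discomfort cannot be Severe, and a clearly noticeable event that needs immediate relief without being overwhelming has no grade. The SAP takes the grade as it stands, so its maximum-severity summaries are open to under-grading and inconsistent grading for BP/pulse increases and mania/hypomania. It would go too far to call those tables wrong for all the AEs of concern, since somnolence and fatigue can be graded and suicidality is reported through the C-SSRS.

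The number of AEs affected cannot be computed from the documents. The conclusion assumes that investigators apply the definitions as written; those who already grade on clinical judgement would reduce the under-grading, but not the inconsistency between raters. The efficacy analyses are not touched. The correction is worth making because the rule is explicit, it bears on events the protocol itself singles out, and it is cheap to repair.

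**What to change.** In Protocol 9.5.5, replace the three definitions with an exhaustive set based on function:

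- Mild: does not interfere with usual activities
- Moderate: interferes to some extent with usual activities
- Severe: prevents usual activities

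Add one sentence: AEs based on measured findings (BP, pulse, weight) and AEs of mania or hypomania are graded on the investigator's judgement of clinical significance and functional impact, not on discomfort.

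Keep severity separate from the seriousness criteria in Protocol 9.5.2; the Severe grade should not borrow from them. The SAP rule for missing severity can stay as it is.

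The cost is a wording change in 9.5.5 and the eCRF completion guide, and a re-check of grades already assigned to BP/pulse and mania/hypomania AEs. Some AEs now graded Mild will move up.

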##### Assessment of Causality

	Protocol 812P413	
	Page 44 of 61	Version 2.0

The Investigator or designee will assess the possibility of a link between the study product and an AE on the basis of the following criteria:

- *Unrelated*
  - There is an evident other explanation for the AE
  - The AE is in accordance with the effect or adverse effect of the concomitant medication being taken by participant
  - The AE occurred prior to the administration of the study product
- *Unlikely relation*
  - Reasonable temporal relationship with the intake of the study product, although there is another plausible explanation for the occurrence of the AE
- *Possible relation*
  - Reasonable temporal relationship with the intake of the study product, although there are a number of other factors that could have caused the AE
- *Probable relation*
  - Reasonable temporal relationship with the intake of the study product although other plausible reasons point to a causal relationship with the study product
- *Definite relation*
  - Reasonable temporal relationship with the intake of the study product, and
  - There is no other explanation for the AE, and
  - Subsidence or disappearance of the AE on withdrawal of the study product (discontinuation), and
  - Recurrence of the symptoms on reintroduction of the study product

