- Analysis of categorical secondary endpoints revealed that the AISRS 30% response rate (defined as the percent of participants with a 30% or more reduction in AISRS Total Score) at Week 6 was significantly higher in the viloxazine ER group compared with placebo (12.4 [0.6, 23.8];  $p = 0.0395$ ); all other comparisons were not significant.

In terms of safety, the most common adverse reactions of Qelbree (occurring at  $\geq 5\%$  and at least twice the placebo rate) were insomnia, headache, somnolence, fatigue, nausea, decreased appetite, dry mouth, and constipation ([Qelbree PI](#)). Adverse events (AEs) leading to discontinuation of Qelbree treatment were fatigue, insomnia, constipation, and headache. Adverse reactions that occurred in at least 2% of patients treated with Qelbree ( $n=189$ ) and more frequently in Qelbree-treated patients than in placebo-treated patients were: insomnia (23% vs 7%), headache (17% vs 7%), nausea (12% vs 3%), dry mouth (10% vs 2%), fatigue (12% vs 3%), decreased appetite (10% vs 3%), and tachycardia (4% vs 1%).

	Protocol 812P413	
	Page 18 of 61	Version 2.0

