To evaluate the effect of Qelbree on executive function in adults with ADHD and comorbid mood symptoms as measured by the BRIEF-A, Self-Report.	Change from baseline at Week 14/EOS in BRIEF-A T-score for the: 
 
• Global Executive Composite (GEC)
 
• Behavioral Regulation Index (BRI)
 
• Metacognition Index (MI)
 
	ADHD-associated impairments in executive function in ADHD is well known. The BRIEF-A is a self-report scale that was validated for evaluating global and aspects of executive function in adults with ADHD. It has been administered in other clinical trials that evaluated the efficacy and safety of ADHD treatments.
To evaluate the effect of Qelbree on aspects of functioning in daily life (work productivity and regular activities) as measured by the WPAI:SHP.	Change from baseline in the WPAI:SHP absenteeism percentage by visit, presenteeism percentage by visit, work productivity percentage by visit, and regular activity percentage by visit.	ADHD-associated functional impairments is well known. The WPAI:SHP is a self-report scale that was validated for evaluating functional impairment in aspects of daily life. It has been administered to assess the impact of ADHD and ADHD treatments on work productivity and regular activities in adults with ADHD.

	Protocol 812P413	
	Page 22 of 61	Version 2.0

Secondary Efficacy		
OBJECTIVES	ENDPOINTS	JUSTIFICATION FOR ENDPOINTS
To evaluate the effect of Qelbree on sleep in adults with ADHD and comorbid mood symptoms as measured by the self-rated PSQI.	Change from baseline at Week 14/EOS in the PSQI global score.	Sleep and/or circadian-related disturbances (e.g., insomnia, daytime sleepiness, delayed sleep phase disorder) have been documented in participants diagnosed with ADHD and in individuals receiving treatment with psychiatric and psychostimulant medication. The PSQI is commonly used in clinical trials to assess changes in sleep parameters (quality, timing, duration, latency, etc.) and overall daytime functioning.

Secondary Safety		
OBJECTIVES	ENDPOINTS	JUSTIFICATION FOR ENDPOINTS

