## 7.2 Exclusion Criteria

A participant who meets any of the following criteria will be excluded from participation in the study:

1. Has a history of substance use disorder (alcohol, opioids, etc.) within the last 6 months prior to providing informed consent with exception of nicotine and cannabis.
2. Is currently taking or has taken Qelbree for treatment of ADHD in the last 3 months or is currently taking another non-stimulant medication for treatment of ADHD, like atomoxetine (Strattera), Clonidine (Catapres, Kapvay) or Guanfacine (Tenex, Intuniv). Stimulant medications for ADHD and most medications for mood symptoms (symptoms of depression and/or anxiety) are allowed.
3. Is taking a prohibited concomitant medication per the Qelbree Prescribing Information.
4. Is a FOCP who is pregnant, nursing, sexually active with a male partner and not willing to use one of the acceptable birth control methods throughout the study and/or is seeking fertility treatment.
5. Has history of moderate or severe head trauma or other neurological disorder or systemic medical disease that, in the Investigator's opinion, is likely to affect central nervous system functioning. This would include participants with:
  - a) A current diagnosis of a major neurological disorder; or
  - b) Seizures, seizure disorder or seizure-like events; or a history of seizure disorder within the immediate family (siblings, parents); or
  - c) Encephalopathy
6. Has attempted suicide within the 6 months prior to the C-SSRS assessment at Screening, or is at significant risk of suicide, either in the opinion of the Investigator or defined as a "yes" to suicidal ideation questions 4 or 5 or answering "yes" to suicidal behavior on the C-SSRS within the 6 months prior to the C-SSRS assessment at Screening.
7. Is currently participating in another clinical trial or has participated in a clinical trial within the 60 days prior to providing informed consent.
8. Has any history of schizophrenia, schizoaffective disorder, or bipolar disorder, or has any other psychiatric disorders in the Investigator's clinical judgement would interfere with their ability to participate in the study.
9. Has any unstable, clinically significant cardiovascular condition that in the Investigator's clinical judgement would preclude their participating in the study.

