#### Unanticipated Problems

##### *Definition*

Unanticipated problems (UAP) involving risks to participants or others includes, in general, any incident, experience, or outcome that meets all of the following criteria:

- Unexpected in terms of nature, severity, or frequency given (a) the research procedures that are described in the protocol-related documents, such as the Institutional Review Board (IRB)-approved research protocol and informed consent document; and (b) the characteristics of the participant population being studied;

	Protocol 812P413	
	Page 45 of 61	Version 2.0

- Related or possibly related to participation in the research (“possibly related” means there is a reasonable possibility that the incident, experience, or outcome may have been caused by the procedures involved in the research); and
- Suggests that the research places participants or others at a greater risk of harm (including physical, psychological, economic, or social harm) than was previously known or recognized.

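### The causality criteria allow an adverse event to be scored unrelated solely because it matches a concomitant drug's effect, and they give no precedence when it also fits a more related category

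*Protocol*

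**What the plan says.** Protocol Section 9.5.5 (Assessment of Causality) has five categories: *Unrelated*, *Unlikely*, *Possible*, *Probable* and *Definite*. Three criteria stand under *Unrelated*: an evident other explanation, onset before the study product, and "The AE is in accordance with the effect or adverse effect of the concomitant medication being taken by participant". *Unlikely* requires reasonable timing, "although there is another plausible explanation for the occurrence of the AE". *Possible* is worded "Reasonable temporal relationship with the intake of the study product, although there are a number of other factors that could have caused the AE".

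SAP 8.1 reduces these to two groups. The relationship "will be classified as unrelated (i.e., unlikely related or not related) or related (possibly related, probably related or definitely related"). It then plans an overview that includes TEAEs by relationship and related serious TEAEs, and a table by system organ class, preferred term and relationship.

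On co-medication, Protocol Section 7.2 states: "Stimulant medications for ADHD and most medications for mood symptoms (symptoms of depression and/or anxiety) are allowed". Section 6.2 asks participants to keep taking their current medications. The secondary safety objective covers Qelbree both as monotherapy and as adjunctive therapy.

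**The concern.** The criterion turns a match with another drug's profile into a sufficient reason for *Unrelated*, even when the event begins soon after Qelbree is started and is also a known Qelbree reaction. Consider a participant on a stable stimulant who develops insomnia on Day 10. That event can be scored *Unrelated*, *Unlikely* or *Possible* on the text as it stands. The first two put it on the unrelated side of the SAP's split and the third puts it on the related side.

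This matters because the trial is open-label, non-randomized and has no reference therapy. The all-causality tables keep every event but have no comparator to separate drug effect from background. The investigator's causality score is the only event-level attribution in the visible plan, and SAP 8.1 reports it.

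**Working it through.** **Are the three *Unrelated* criteria alternatives?** Sections 9.4.1 and 9.5.3 both start AE collection at the first dose. An AE that precedes the study product is therefore not collected, so if all three criteria were required together, no collected AE could ever be *Unrelated*. The lines under *Definite* are joined by an explicit *and*; those under *Unrelated* are not. Each *Unrelated* criterion is therefore sufficient alone.

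**Do the categories overlap?** For an event with reasonable timing to Qelbree that is also a known effect of a concomitant drug:

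| Category | Met? | SAP 8.1 group |
|---|---|---|
| *Unrelated* | Yes, by the concomitant-drug criterion | Unrelated |
| *Unlikely* | Yes, if the drug is a plausible explanation | Unrelated |
| *Possible* | Can be, if other factors could be the cause | Related |

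Neither document states a precedence.

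**Which reactions do the documents show to be shared?** The PSQI justification in Protocol Section 4 says that sleep disturbances, with insomnia and daytime sleepiness among its examples, are documented in ADHD and in "individuals receiving treatment with psychiatric and psychostimulant medication". Insomnia has the highest rate of the reactions listed in Section 3.2.2 (23% on Qelbree, 7% on placebo). Section 3.3.1 gives somnolence as 6% against 2%. No adverse-effect profile of the concomitant drugs is given for headache, nausea, fatigue or the other reactions.

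**Size (illustration).** The plan gives no figure on relatedness. The only planned number used is up to 750 dosed. It agrees with the stated completers: 750 × (1 − 0.33) = 502.5, against up to 500.

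Inputs:
- p = 0.23, the insomnia rate in the earlier 6-week adult trial. That trial excluded depression and anxiety, so the rate here may differ.
- a = share of participants on an overlapping drug. Not given; assumed 25%, 50% or 75%.
- u = share of their insomnia events scored *Unrelated* or *Unlikely*. Not given; assumed 0%, 50% or 100%, where 100% is the criterion applied literally.

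Formula: related rate = p × (1 − a × u). It starts from at most 23%, which supposes that every insomnia event would otherwise be scored related.

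| a | u = 0% | u = 50% | u = 100% | Participants moved at u = 100% (750 × 0.23 × a) |
|---|---|---|---|---|
| 25% | 23% | 20.1% | 17.25% | 43 |
| 50% | 23% | 17.25% | 11.5% | 86 |
| 75% | 23% | 14.4% | 5.75% | 129 |

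Somnolence at 6% falls to 4.5%, 3.0% or 1.5% at u = 100%. The all-causality rates stay at 23% and 6% in every cell.

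**Would such events usually be background?** In the earlier trial (23 − 7)/23 = 0.696, so about 70% of insomnia cases on Qelbree were in excess of placebo. If that carried over, scoring all insomnia in co-medicated participants as unrelated would be wrong for most of them.

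**The case against.** The strongest reply is that the criteria guide a judgment and do not fix a score. An investigator may choose *Possible* for the event described, and then nothing is lost. This stands: the defect permits a downward bias but does not guarantee one, and the lower end of the range is zero. The result nevertheless depends on a choice that the protocol leaves open, and one stated criterion points the wrong way.

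The reply also says, correctly, that the safety endpoint is adverse events, not related adverse events. The all-causality, most-common, severity, serious and withdrawal tables count each event whatever its relationship. Misclassified events change column in the relationship table and leave the related-serious count; they do not disappear. The SAP also counts missing relatedness as definitely related, which is conservative, but that does not help where a score has been given.

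The documents do not support four stronger readings that a reader might draw:

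- *Qelbree's common reactions as a group are lost from the related tables.* The overlap is documented for insomnia and daytime sleepiness only.
- *Escalation of serious events is compromised.* Section 9.5.3 requires all AEs to be reported whatever their relationship, and Section 9.5.4 sends SAEs to the sponsor within 24 hours with no causality filter. The unanticipated-problem test, "Related or possibly related to participation in the research", carries its own definition of possibly related and is not tied to the 9.5.5 score.
- *Adjunctive use will look safer than monotherapy.* The visible text plans no TEAE comparison by monotherapy or adjunctive use. The exploratory sections are blank in the public copy, so nothing can be inferred from them.
- *Only adjunctive users are exposed.* The criterion covers any concomitant medication, and adjunctive therapy is not defined.

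**Conclusion.** The concern holds as a defect in the causality wording. Section 9.5.5 makes a concomitant-drug match sufficient for *Unrelated* without asking whether Qelbree is also plausible, the categories overlap without precedence, and SAP 8.1 carries the outcome into the related-TEAE and related-serious-TEAE summaries. The possible bias is downward and confined to participants taking concomitant drugs.

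For insomnia the related share could fall by anything from nothing to three quarters (23% to 5.75%). That range rests on assumed values for the share on an overlapping drug and for investigator behavior, and on a rate from a different population. This should be fixed. It is not critical, because the study is descriptive with no formal hypotheses and the all-causality results are intact.

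**What to change.** 1. Reword the criterion in Protocol Section 9.5.5: *The AE is explained by a concomitant medication and there is no reasonable possibility that the study product caused or contributed to it.*
2. Add a precedence rule: when an AE meets more than one category, the more related category applies. This fits SAP 8.1, which already counts the most related occurrence when a participant has several events under one preferred term.
3. Before database lock, have the investigator re-review AEs scored *Unrelated* under the present criterion. The SAP cannot recover attribution from the collapsed scores afterwards.

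A blanket rule that any event arising after first dose on stable co-medication is at least *Possible* is not recommended. It would replace one mechanical rule with another that pushes relatedness upward, and Section 4 links sleep disturbance to ADHD itself.

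The cost is a few sentences in the protocol, a note to the investigator and the re-review. The reported rate of related events is likely to rise somewhat.
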